14.4. Level of Statistical Significance

All planned analysis for this study will be conducted with an overall type I error rate of 5%. Due to the exploratory nature of the study, adjustment for multiple comparison will not be performed.

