14.2. Sample Size Justification

This is a pilot study for assessing the investigational test articles. As such, the sample size was not determined based on any power analysis with regard to the primary endpoint. The collected data will be used to design future trials.

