14.5. Primary Analysis

Primary efficacy analysis:

Distance and near wavefront aberration, specifically, spherical aberration (Z_4^0), will be analyzed using a linear mixed model. Each model will include the experimental design factors: treatment, distance and treatment by distance interaction and subject as random effect. Other baseline characteristics known of importance such as age and gender will be included as fixed covariates when appropriate. Kenward and Roger method will be used for the calculation of the denominator of degrees of freedom.³⁶

Comparisons between the treatment groups will be carried out using 95% confidence intervals constructed of least-square means (LSM) differences (RMY-100 minus OK) from the linear mixed models at each distance. Statistical difference will be concluded in the lower limit is greater than 0 or the upper limit is less than 0.

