14.6. Secondary Analysis

Secondary efficacy analysis:

Off-axis refraction at $\pm 30^{\circ}$ retinal eccentricities with targets at both distance (4 m) and near (25 cm) will be analyzed using a linear mixed model. Each model will include the experimental design factors: treatment, distance and treatment by distance interaction and subject as random effect. Other baseline characteristics known of importance such as age and gender will be included as fixed covariates when appropriate. Kenward and Roger method will be used for the calculation of the denominator of degrees of freedom.³⁶

Comparisons between the treatment groups will be carried out using 95% confidence intervals constructed of least-square means (LSM) differences (RMY-100 minus OK) from the linear

mixed models at each distance. Statistical difference will be concluded in the lower limit is greater than 0 or the upper limit is less than 0.

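### Section 14.4 calls 5% the overall type I error rate, but without multiplicity adjustment 5% is only the level of each comparison

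*Combined protocol and SAP*

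**What the plan says.** Section 14.4 has two sentences. The first reads "All planned analysis for this study will be conducted with an overall type I error rate of 5" per cent. The second reads "Due to the exploratory nature of the study, adjustment for multiple comparison will not be performed".

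Section 14.5 gives the primary analysis: "Distance and near wavefront aberration, specifically, spherical aberration (Z_4^0), will be analyzed using a linear mixed model". On how the groups are compared it says "Comparisons between the treatment groups will be carried out using 95% confidence intervals constructed of least-square means (LSM) differences", taken "from the linear mixed models at each distance". The decision rule is "Statistical difference will be concluded in the lower limit is greater than 0 or the upper limit is less than 0". Section 14.6 applies the same model and rule to off-axis refraction at 30 degrees either side of fixation: "retinal eccentricities with targets at both distance (4 m) and near (25 cm) will be analyzed using a linear mixed model".

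Section 2.3 lists two primary hypotheses (distance and near spherical aberration) and two secondary ones (distance and near off-axis refraction). Section 14.8 says that interim analysis does not apply. Section 2.1 calls the study exploratory, and Section 14.2 says "This is a pilot study for assessing the investigational test articles" and that no power calculation was used.

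**The concern.** In its usual sense, an overall type I error rate is the probability of at least one false positive across the set of analyses. The first sentence of 14.4 claims 5% for that probability. The second sentence rules out the adjustment that would be needed to achieve it, and the interval rule in 14.5 and 14.6 supplies no substitute. The two sentences therefore conflict.

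What is at stake is how the results are described. Section 21 expects publication in peer-reviewed journals, and Section 14.2 says the data will inform the design of later trials. If the first sentence is carried into a report, readers will be told of error control that the analysis does not have.

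**Working it through.** **Inputs.**
- Stated overall rate: 5% (14.4).
- Level of each interval: 95%, two-sided (14.5, repeated in 14.6).
- Primary comparisons: 2, distance and near (14.5; matches 2.3).
- Secondary comparisons: 2, distance and near (14.6; matches 2.3). There would be 4 if +30 and -30 degrees were tested separately, which 14.6 does not say.
- Adjustment, hierarchy, gate or joint rule: none (14.4 to 14.6). Interim looks: none (14.8).
- Correlation between the test statistics: not given in the documents. Assumed values are shown as a range.

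**Step 1: reproduce the plan's figure.** A two-sided 95% interval excludes a true difference of zero with probability 1 - 0.95 = 0.05. The 5% is thus reproduced for one comparison.

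**Step 2: independent comparisons.** With every true difference zero, the chance that at least one of k intervals excludes zero is 1 - 0.95^k:
- k = 2: 1 - 0.95^2 = 0.0975
- k = 4: 1 - 0.95^4 = 0.1855
- k = 6: 1 - 0.95^6 = 0.2649

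The Bonferroni bound, k × 0.05, holds under any dependence: 0.10, 0.20 and 0.30.

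**Step 3: correlated comparisons.** Distance and near readings come from the same eyes, so positive correlation is likely. For jointly normal statistics with a common correlation ρ, critical value c = 1.96, and φ and Φ the standard normal density and distribution function, the rate is

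1 - ∫ φ(s) · [Φ((c - √ρ·s)/√(1-ρ)) - Φ((-c - √ρ·s)/√(1-ρ))]^k ds.

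| Comparisons | Independent | ρ = 0.5 | ρ = 0.8 |
|---|---|---|---|
| 2 (primary) | 9.75% | 9.1% | 7.8% |
| 4 (primary and secondary) | 18.5% | 15.6% | 11.4% |
| 6 (only if +30 and -30 degrees are tested separately) | 26.5% | 20.7% | 13.9% |

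At ρ = 0.9 the two primary comparisons still give 7.0%. The rate comes down to 5% only at perfect correlation.

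**Step 4: check at the planned size.** This used 400,000 simulated null trials with the targeted completers (20 Test, 15 Control). A pooled t interval at each distance (20 + 15 - 2 = 33 degrees of freedom) stood in for the mixed-model interval without covariates. At least one false primary difference occurred in 9.7%, 9.1% and 7.9% of trials at correlations 0, 0.5 and 0.8. The rate per comparison was 5.0%. The small samples do not change the result.

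**Step 5: other meanings of overall.** It cannot refer to spending alpha over interim looks, since there are none. A rule requiring a difference at both distances would hold the rate at 5% or less, but the plan states no such rule.

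**The case against.** The strongest reply is that 14.4 corrects itself. The second sentence openly says there is no adjustment, and overall may have been meant loosely as one 5% level used throughout. That reading fits the 95% intervals, and in an exploratory pilot no decision rests on the point. This limits the harm and keeps the severity low. It does not make the first sentence true, because disclosing the absence of adjustment is what shows the overall rate to be uncontrolled. If a general per-comparison level was intended, the sentence should say so.

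A second reply uses Section 2.3, where the primary hypotheses predict that RMY-100 will be no lower than orthokeratology. If those are taken as the nulls, only an upper limit below zero is an error. That is 2.5% at each distance, so at most 5% for the two primaries (1 - 0.975^2 = 4.94% if independent). But 14.5 declares a difference in either direction. Even on this reading, four comparisons give 1 - 0.975^4 = 9.6% if independent.

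Two cautions about the figures stand. First, 9.75% is the value under independence, and positive correlation lowers it; for jointly normal statistics it is a ceiling, while the bound free of assumptions is 10%. Second, the six-comparison row is hypothetical: eccentricity is not a factor in the 14.6 model and 2.3 lists two secondary hypotheses, so four comparisons is the more direct count.

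**Conclusion.** The concern holds, at minor severity. As written, the overall 5% in 14.4 is a property the analysis does not have; 5% is the two-sided level of each comparison. Across the two primary comparisons the rate is 9.75% under independence and about 7.8% to 9.1% at assumed correlations of 0.8 to 0.5. Across four comparisons it is 18.5% under independence and 11.4% to 15.6% over the same range. These figures assume that all true differences are zero, that the statistics are jointly normal, and that a difference in either direction counts, as 14.5 states. The correlations are assumptions. The conclusion does not depend on their exact value, since only perfect correlation would return 5%. The decision not to adjust is sound for this study and is not in question.

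**What to change.** Replace the first sentence of 14.4 with: *Each comparison will use a two-sided 5% level (95% CI); the overall type I error rate across comparisons is not controlled and may reach about 9.8% for the two primary comparisons.* Keep the second sentence, which gives the exploratory purpose as the reason for not adjusting. Carry the same wording into the report and any publication.

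The cost is one sentence. Sections 14.5 and 14.6, the data, the sample size and the subjects' procedures are unaffected. The stated error rate becomes less favourable but correct.

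If the sponsor does want 5% overall, the intervals would have to widen. Bonferroni gives 97.5% intervals for the two primary comparisons (0.05/2 = 0.025 each) or 98.75% intervals for four (0.05/4 = 0.0125 each). That is not needed for a study of this purpose.

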14.5. Primary Analysis

Primary efficacy analysis:

Distance and near wavefront aberration, specifically, spherical aberration (Z_4^0), will be analyzed using a linear mixed model. Each model will include the experimental design factors: treatment, distance and treatment by distance interaction and subject as random effect. Other baseline characteristics known of importance such as age and gender will be included as fixed covariates when appropriate. Kenward and Roger method will be used for the calculation of the denominator of degrees of freedom.³⁶

Comparisons between the treatment groups will be carried out using 95% confidence intervals constructed of least-square means (LSM) differences (RMY-100 minus OK) from the linear mixed models at each distance. Statistical difference will be concluded in the lower limit is greater than 0 or the upper limit is less than 0.

14.6. Secondary Analysis

Secondary efficacy analysis:

Off-axis refraction at $\pm 30^{\circ}$ retinal eccentricities with targets at both distance (4 m) and near (25 cm) will be analyzed using a linear mixed model. Each model will include the experimental design factors: treatment, distance and treatment by distance interaction and subject as random effect. Other baseline characteristics known of importance such as age and gender will be included as fixed covariates when appropriate. Kenward and Roger method will be used for the calculation of the denominator of degrees of freedom.³⁶

Comparisons between the treatment groups will be carried out using 95% confidence intervals constructed of least-square means (LSM) differences (RMY-100 minus OK) from the linear

mixed models at each distance. Statistical difference will be concluded in the lower limit is greater than 0 or the upper limit is less than 0.

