2.2. Endpoints

Primary Endpoint

The primary endpoint of this study is wavefront aberrations measured at 4-meter distance (0.25 D target vergence) and near (25 cm with 4 D target vergence).

Secondary Endpoint

The secondary endpoint of this study is Off-axis refraction at both temporal and nasal fields of retina at $\pm 10^{\circ}$, $\pm 20^{\circ}$, $\pm 30^{\circ}$ with targets at 4 meters and $\pm 30^{\circ}$ only with targets at 25 cm.

Other Exploratory Endpoints and observations include:

- Corneal and test article on-eye topography
- Accommodative response with target vergence of 0.25 D, 1 D, 2 D, 3 D and 4 D
- Slit lamp findings
- LogMAR visual acuity under HLHC, LLHC, and HLLC conditions
- Lens fit assessment
- Subjective vision assessment (CLUE Vision)

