2.3. Hypotheses

Primary Hypotheses:

- 1. After the 10-minute lens settling period, distance (4 meters) spherical aberration (Z_4^0) measured with RMY-100 on the eye will be similar or larger than that measured from the post-OK eyes.
- 2. After the 10-minute lens settling period, near (25 cm) spherical aberration (Z_4^0) measured with RMY-100 on the eye will be similar or larger than that measured from the post-OK eyes.

Secondary Hypotheses:

- 1. After the 10-minute lens settling period, distance (4 m) off-axis refraction at $\pm 30^{\circ}$ retinal eccentricity measured with RMY-100 on the eye will be similar or larger than that measured from the post-OK eyes.
- 2. After the 10-minute lens settling period, near (25 cm) off-axis refraction at $\pm 30^{\circ}$ retinal eccentricity measured with RMY-100 on the eye will be similar or larger than that measured from the post-OK eyes.

Other Hypotheses:

- 1. After the 10-minute lens settling period, the slope of accommodative response measured with RMY-100 on the eye will be similar as that measured from the post-OK eyes.
- 2. After the 10-minute lens settling period, distance (4 m) and near (25 cm) wavefront aberrations, off-axis refractions within $\pm 30^{\circ}$ retinal eccentricity, and the slope of accommodative response measured with RMY-100 on the eye will be different from that measured with spectacle trial lenses on eye.

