4. STUDY DESIGN AND RATIONALE

4.1. Description of Study Design

This is a two-arm parallel, non-masked, bilateral, non-dispensing study with one Test arm and one concurrent, non-randomized Control arm.

For subjects enrolled in the Test arm, investigational test articles will be bilaterally fitted to the subject's eyes. Concurrently, a smaller sample of subjects who are established orthokeratology lens wearers will be enrolled to Control arm. Endpoint measures will be collected over one eye only (Test arm: OD only; Control arm: better OK fitted eyes, eg, better centration and better myopia correction outcome, etc., based on the investigator's judgement. If both eyes are treated equally well, choose OD).

For subjects in the Test arm, there will be a total of 2 visits: Visit 1: Screening, baseline endpoint measures with bare eye/spectacle trial lenses Visit 2: Lens fitting, endpoint measures over the study lenses and final evaluation.

For the Control arm, the investigators will pre-identify subjects through reviewing the case history of existing orthokeratology treated patients. Only subjects with complete pre-treatment record, e.g., spherocylindrical refraction and corneal topography will be invited to participate in the study.

For subjects in the Control arm, there will be a total of 1 visit: Visit 1: Screening, baseline and endpoint measures over the selected eyes.

Study participants will have no access to test articles at study closure.

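### Section 14.6 has no nasal/temporal field term, so on its most natural reading the ±30° contrast averages the two fields and cannot show a difference confined to one of them

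*Combined protocol and SAP*

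**What the plan says.** Section 2.2 defines the secondary endpoint as "Off-axis refraction at both temporal and nasal fields of retina at" ±10°, ±20° and ±30° for the 4 m target, and ±30° only for the 25 cm target. Each subject therefore supplies two 30° values per target distance, one from each field.

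Section 14.6 states that off-axis refraction at ±30° "retinal eccentricities with targets at both distance (4 m) and near (25 cm) will be analyzed using a linear mixed model". It gives the terms as follows: "Each model will include the experimental design factors: treatment, distance and treatment by distance interaction and subject as random effect". Age and gender may be added as covariates. Least-square mean differences, RMY-100 minus OK, come from the "mixed models at each distance". No field term is listed, no contrast is defined per field, and the section does not say how +30° and −30° are combined.

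Section 2.3 states two secondary hypotheses, one for distance and one for near. In each, off-axis refraction at ±30° "retinal eccentricity measured with RMY-100 on the eye will be similar or larger than that measured from the post-OK eyes". Neither is split by field.

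Section 4.1 fixes the measured eye: "Test arm: OD only; Control arm: better OK fitted eyes". A Control eye may therefore be a left eye, while every Test eye is a right eye.

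**The concern.** The endpoint distinguishes nasal from temporal retina, but the model as listed does not. If both values per subject and distance enter one model with these terms, the treatment contrast at a distance estimates the mean of the nasal and temporal differences. Two things follow.

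- **Cancellation and dilution.** Arm differences of opposite sign in the two fields offset each other, and a difference present in one field is halved.
- **Residual inflation.** A mean nasal-temporal gap common to both arms has no term to absorb it, so it is counted as residual variation.

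The first matters more. Section 1 gives the shift of peripheral retinal focus as the commonly believed mechanism of orthokeratology, and reports that the lens designed to simulate it was largely ineffective. Section 2.1 sets out to understand the difference in optical impact between the two, and section 14.2 says that the data will be used to design future trials. A contrast that cannot separate the fields discards part of what the off-axis measurements were taken to show.

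**Working it through.** The plan gives no SD, effect size, asymmetry or interval width, so it has no figure to reproduce.

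**Inputs from the documents.** Target completers are 20 Test and 15 Control (section 4.3), so N = 35. There are four cells per subject (two fields × two distances), two-sided 95% intervals, and the model terms of section 14.6.

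**Assumptions.** One mean per subject-field-distance cell, because the plan does not say how the three repeats enter. Between-subject SD σs and residual SD σe are set as shown below. D is a nasal-temporal gap in the means, common to both arms. Satterthwaite degrees of freedom stand in for Kenward-Roger.

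**Step 1: which reading.** The phrase "Each model" in 14.6 could mean one model per eccentricity. Section 14.5 uses the same phrase where the outcome is a single coefficient: "specifically, spherical aberration (Z_4^0), will be analyzed using a linear mixed model. Each model will include". The phrase therefore gives no evidence of separate models by field. Section 14.6 also speaks of one model for plural eccentricities, and both its contrasts and the hypotheses are one per distance. Pooling is the better reading, but it is inferred.

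**Step 2: what the pooled contrast estimates.** With balanced cells, contrast = (nasal difference + temporal difference)/2.

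- (+1 − 1)/2 = 0 D.
- (+1 + 0)/2 = 0.5 D.

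Simulation with 4,000 runs per row, σs = 1.0 D and σe = 0.5 D, gave:

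| True difference, nasal / temporal | D | Mean pooled estimate | Pooled interval excludes 0 | Field-specific interval excludes 0 |
|---|---|---|---|---|
| +1 / −1 | 0 | 0.005 D | 3.2% | 71% nasal, 71% temporal |
| +1 / 0 | 1 D | 0.50 D | 21% | 72% nasal |

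**Step 3: precision lost by omitting field.**

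- Between-subject mean square: MSB = 4σs² + σe².
- Residual mean square with field in the model: MSE = σe².
- Residual mean square with field omitted: MSE = σe² + N·D²/(3N − 2) = σe² + 35D²/103.
- Variance of the contrast at one distance: (1/20 + 1/15)(MSB + MSE)/4.

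At D = 1 D the addition is 35/103 = 0.340, so with σe = 0.5 the residual mean square rises from 0.250 to 0.590.

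- σs = 1.0, σe = 0.5: MSB = 4.25. SE ratio = √(4.840/4.500) = 1.037. After the change in degrees of freedom (37.0 to 42.5), the half-width goes from 0.734 to 0.758 D, which is 3.2% wider.
- σs = 0.5, σe = 0.5: MSB = 1.25. SE ratio = √(1.840/1.500) = 1.107, or 11%. After the change in degrees of freedom (46.9 to 66.7), the interval is about 10% wider.

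With σs = 1.0 and σe = 0.5, the widening at other gaps is 0% at D = 0, 0.8% at 0.5 D and 12.6% at 2 D. Simulated coverage with no treatment difference was 95.1%, 96.2% and 97.4% at D = 0, 1 and 2 D, so under this structure the interval is conservative.

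**Step 4: what separating the fields costs.** The variance of a field-specific contrast is proportional to σs² + σe², and that of the average to σs² + σe²/2. For σs = 1.0 and σe = 0.5 the SE ratio is √(1.25/1.125) = 1.054. For both SDs 0.5 it is √(0.50/0.375) = 1.155. A field-specific contrast is therefore about 5% to 15% less precise than the average.

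**The case against.** The strongest reply is that the plan never states that it pools. Section 14.6 uses both a singular and a plural for its models, and if one were fitted per field neither consequence would follow. This stands to the extent that pooling is a reading. It does not help the plan, because the separate-model intention would then have to be written, along with contrasts per field.

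A second reply is that one contrast per distance matches the hypotheses in 2.3, in a pilot that is exploratory and not powered. That is right, and it is why the field average should stay. It does not explain why an endpoint naming two fields has no result for either.

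Four stronger readings are tempting, and the documents do not support them.

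- **That the planned interval is necessarily too wide.** The widening needs an asymmetry that the documents do not give. Other unmodelled structure can act the other way: with an assumed subject-by-distance SD of 1.0 D, σs = 1.0 and σe = 0.5, the model SE is 0.92 of the true SE at D = 0 and 0.94 at D = 1 D.
- **That nasal and temporal values will be mixed between arms because a Control eye may be OS.** The procedures list signed angles, but the endpoint names the fields anatomically, and the autorefractor instruction in Appendix D, which may define the coding, is not readable in this copy.
- **That decentred orthokeratology treatment will appear as a nasal-temporal difference.** Section 4.1 mentions centration only as one basis for choosing the eye.
- **That the plan would declare the arms similar when the fields differ in opposite directions.** Section 14.6 says only when a statistical difference is concluded; it has no rule for similarity.

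**Conclusion.** The point holds in this form: with the terms listed in 14.6, the model cannot separate a nasal from a temporal treatment difference, although the endpoint names both fields. Under pooling, opposite-sign differences cancel and a difference in one field is halved. That follows from the averaging and does not depend on the SDs; the detection rates of 3.2% against 71%, and 21% against 72%, do.

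The loss of precision is secondary and conditional. It is zero without asymmetry. At a 1 D gap it is about 3% with subject SD 1.0 D, and about 11% in standard error (10% in interval width) with subject SD 0.5 D, taking residual SD 0.5 D in both cases. These SDs and the gap are assumptions. The point concerns a secondary endpoint in a pilot and does not touch the primary analysis. It is worth correcting because the change is cheap and the measurements are already scheduled.

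**What to change.** In section 14.6, add field (nasal/temporal), treatment-by-field and treatment-by-field-by-distance as fixed effects, or state that one model is fitted per field. The parts do different work: a field main effect removes a shared asymmetry from the residual but leaves the pooled estimate unchanged, and only the treatment-by-field terms or field-specific models prevent cancellation.

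Define field anatomically, with the mapping from signed angle to nasal or temporal given for right and left eyes, since Control eyes may be OS. Say also whether the three repeats are averaged or entered separately.

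Report RMY-100 minus OK at nasal 30° and at temporal 30° for each target distance, and keep the field-averaged contrast per distance that answers the hypotheses in 2.3.

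The cost is SAP wording and no extra measurement. There would be six exploratory contrasts (four field-specific and two averages) instead of two. Section 14.4 plans no multiplicity adjustment, so they should be presented as descriptive. Each field-specific contrast is somewhat less precise than the average.
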